9.5.1. Immunogenicity Analyses

The primary analysis population for immunogenicity will be the PP Set, unless otherwise specified. If the number of participants in the FAS and PP Set differs (defined as the difference divided by the total number of participants in the PP Set) by more than 10%, supportive analyses of immunogenicity may be conducted using the FAS.

The coprimary endpoints include the GMT of RSV-A/RSV-B nAb titers at Day 22 (Arm 1) and Day 43 (Arm 2) and GMT of anti-HA Ab titers at Day 22 for each influenza strain. For each coprimary endpoint regarding GMT, the GMR will be estimated using an analysis of covariance model on the log-transformed titers, with the treatment group and log-transformed baseline titers as a fixed covariate, adjusted for stratified age group used for randomization. The GLSM and its corresponding 95% CI in a log-transformed scale estimated from the model will be back-transformed to obtain these estimates in the original scale as an estimate of the GMT and its 95% CI. The GMR, estimated by the ratio of the GLSM and the corresponding 2-sided 95% CI, will be provided to assess the treatment difference. The corresponding 2-sided 95% CI of the GMR will be provided to assess the difference in the immune response between the 2 treatment groups. For each coprimary endpoint regarding GMT, the noninferiority of the GMT will be demonstrated if the LB of the 95% CI of the GMR is >0.667.

The SRR of RSV-A/RSV-B nAbs is defined as proportion of participants with postvaccination titers $\ge 4 \times \text{LLOQ}$ if baseline is $\le \text{LLOQ}$ or a ≥ 4 -fold increase from baseline if baseline is $\ge \text{LLOQ}$. The SCR of an influenza strain is defined as proportion of participants with a postvaccination

titer \ge 1:40 if baseline is \le 1:10 or a \ge 4-fold rise in postvaccination HAI Ab titer if baseline is \ge 1:10.

The number and percentage of participants with SRR at Day 22 (Arm 1) and Day 43 (Arm 2) or SCR at Day 22 will be provided with 2-sided 95% CI using the Clopper-Pearson method. For secondary endpoints regarding SRR and SCR, the Miettinen-Nurminen's method will be used to calculate the 95% CI for the difference in the SRR or SCR at corresponding timepoint between the treatment groups. For each strain, the noninferiority of SRR or SCR will be considered demonstrated if the LB of the 95% CI of the SRR or SCR difference is >-10% based on a noninferiority margin of 10%.

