3.2. Secondary Endpoints

The secondary immunogenicity objectives will be evaluated by the following endpoints:

- Seroresponse rate (SRR) in RSV-A and RSV-B nAbs at Day 22 (Arm 1) or Day 43 (Arm 2).
 - Seroresponse is defined as a postinjection titer $\ge 4 \times LLOQ$ if baseline is < LLOQ or a ≥ 4 -fold increase from baseline if baseline is $\ge LLOQ$.
- Geometric mean fold rise (GMFR) of postinjection RSV-A and RSV-B nAbs (Day 22 for Arm 1 and Day 43 for Arm 2) compared to baseline (Day 1 for Arm 1 and Day 22 for Arm 2).
- Proportion of participants with ≥2-fold increase in RSV-A and RSV-B nAbs at Day 22 (Arm 1) or Day 43 (Arm 2).
- Seroconversion rate (SCR) in influenza anti-HA Abs as measured by HAI assay at Day 22.
 - Seroconversion is defined as a postinjection titer ≥1:40 if baseline is <1:10 or a
 ≥4-fold rise from baseline in postinjection titer if baseline is ≥1:10.
- GMFR of postinjection influenza anti-HA Abs at Day 22 compared to baseline (Day 1) as measured by HAI assay.

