6.4.2.1. Primary Analysis Approach

The coprimary endpoints include the following:

- GMT of serum RSV-A and RSV-B nAbs at Day 22 (Arm 1) and Day 43 (Arm 2)
- GMT of serum influenza anti-HA Abs as measured by HAI assay at Day 22

The statistical analyses are:

• For each coprimary endpoint, the GMR will be estimated using an analysis of covariance (ANVOVA) model on the log-transformed titers, with the treatment group and log-transformed baseline titers as the fixed covariate, adjusted for stratified age group used for randomization. The geometric least square mean (GLSM) for each treatment group and its corresponding 95% CI in a log-transformed scale will be estimated from the model and back-transformed to obtain these estimates in the original scale as an estimate of the GMT and its 95% CI. The GMR estimated by the ratio of the GLSMs and the corresponding 2-sided 95% CI will be provided to assess the treatment difference in the immune response between the 2 treatment groups. For each coprimary endpoint, the

noninferiority of the GMT will be demonstrated if the LB of the 95% CI of the GMR is >0.667 based on a noninferiority margin of 1.5.

• Additionally, GMT of RSV-A nAb, RSV-B nAb, and influenza anti-HA Abs for each influenza strain with corresponding 95% CI will be provided at each visit (as applicable) by treatment group. The 95% CIs will be calculated based on the t-distribution of the log-transformed values and then back transformed to the original scale for presentation. The following descriptive statistics will also be provided at each visit: the number of participants (n), median, minimum and maximum. GMT with 95% CI will be plotted at each visit (as applicable) by treatment group.

The study is considered to meet the primary immunogenicity objective if the noninferiority of the immune response to mRNA-1345 coadministered with Fluzone HD is met based on all the coprimary endpoints.

The above analysis corresponds to the Primary Immune Estimands 1a-2a as described in Appendix G, Table 5.

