6.4.3. Analysis of the Secondary Immunogenicity Endpoints

The secondary endpoints include the following:

- SRR in RSV-A and RSV-B nAbs at Day 22 (Arm 1) or Day 43 (Arm 2)
- GMFR of RSV-A and RSV-B nAbs at Day 22 (Arm 1) or Day 43 (Arm 2) compared to baseline (Day 1 for Arm 1 or Day 22 for Arm 2)
- Proportion of participants with ≥2-fold increase in RSV-A and RSV-B nAbs at Day 22 (Arm 1) or Day 43 (Arm 2) compared to baseline (Day 1 for Arm 1 or Day 22 for Arm 2)
- SCR in influenza anti-HA Abs for each influenza strain at Day 22
- GMFR of influenza anti-HA Abs for each influenza strain at Day 22 compared to baseline (Day 1)

The statistical analyses are:

• SRR in RSV-A and RSV-B nAbs at Day 22 (Arm 1) or Day 43 (Arm 2) will be provided with 2-sided 95% CIs by treatment group using the Clopper-Pearson method. The SRR

difference between the two treatment groups will be provided with 2-sided 95% CIs using the Miettinen-Nurminen's method. For each RSV subtype, the noninferiority of the SRR will be demonstrated if the LB of the 95% CI of the SRR difference is >-10% based on the noninferiority margin of 10%.

- SCR in influenza anti-HA Abs for each influenza strain at Day 22 will be provided with 2-sided 95% CIs by treatment group using the Clopper-Pearson method. The SCR difference between the two treatment groups will be provided with 2-sided 95% CIs using the Miettinen-Nurminen's method. For each influenza strain, the noninferiority of the SCR will be demonstrated if the LB of the 95% CI of the SCR difference is >-10% based on the noninferiority margin of 10%.
- GMFR of RSV-A and RSV-B nAbs at Day 22 (Arm 1) or Day 43 (Arm 2) compared to baseline (Day 1 for Arm 1 or Day 22 for Arm 2), and GMFR of influenza anti-HA Abs at Day 22 compared to baseline (Day 1) will be provided with corresponding 95% CI by treatment group. The 95% CIs will be calculated based on the t-distribution of the difference in the log-transformed values (postbaseline time point baseline) and then back transformed to the original scale for presentation. GMFR with 95% CI will be plotted by treatment group.
- Proportion of participants with ≥2-fold increases in RSV-A and RSV-B nAbs at Day 22
 (Arm 1) and Day 43 (Arm 2) compared to baseline (Day 1 for Arm 1 and Day 22 for Arm
 2) will be provided with 2-sided 95% CIs by treatment group using the Clopper-Pearson method.

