6.5. Multiplicity Adjustment

A sequential/hierarchical testing procedure will be used to control the overall Type 1 error rate at 0.05 (2-sided) over the primary endpoints, and secondary endpoints.

The coprimary endpoints will be tested at the planned primary analysis at a 2-sided Type 1 error rate of 0.05. The success criteria of all 6 coprimary endpoints need to be met in order to declare the study a success to achieve noninferiority of coadministration.

The secondary endpoints on SRR and SCR will only be tested at the primary analysis at a 2-sided Type 1 error rate of 0.05 when all coprimary endpoints have achieved statistical significance. The secondary endpoints will be tested sequentially in the following order: 1) SCR of influenza anti-HA Abs for each influenza strain, 2) SRR of RSV-A nAbs and 3) SRR of RSV-B nAbs.

No further testing will be performed once the sequence/hierarch breaks, that is, further testing stops as soon as an endpoint in the sequence fails to meet success criterion of noninferiority. Analyses of remaining other secondary immune endpoints are not controlled for multiplicity.

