- A complete physical examination, including height and weight, will be performed at the Screening Visit. Symptom-directed physical examinations will be performed at other study visits, if clinically indicated (see protocol Section 8.3.1 for additional details).
- d. Vital sign measurements include assessment of systolic and diastolic blood pressure, pulse rate, respiratory rate, and body temperature (preferred route is oral) (see protocol Section 8.3.2 for additional details).
- Blood samples for humoral immunogenicity must be collected prior to administration of the study intervention on Day 1 and Day 22.
- All participants will be randomized to receive 2 IM injections, one in each arm, in the deltoid muscle (Day 1) and 1 IM injection in the deltoid muscle (Day 22).
- At Day 1 and Day 22, eDiary instruction will be provided while the participant is onsite. The participant will be required to make eDiary entries approximately 30 minutes after each vaccination while at the study site and again that same evening when at home. Study participants will continue to record in the eDiary each day at the same time for 6 days following each vaccination. Local solicited ARs will be recorded separately for each injection. eDiary review by the site should occur daily on Day 1-Day 7 and Day 22-28. Additional review of the eDiary will occur at Day 8 and Day 29 between the site and the participant during the safety telephone calls.
- h. Medically qualified study staff will contact all participants. The participant will be interviewed according to the script. Information will be collected about occurrence of unsolicited AEs through 21 days postvaccination for either RSV or influenza, and the occurrence of MAAEs, SAEs,

Confidential Page 40
Document Number: VV-CLIN-015611 eDMS Version: 2.0

AESIs, or AEs leading to study discontinuation and concomitant medications associated with those events, and receipt of any nonstudy vaccinations at all points of contact.

Date Issued: 10-Nov-2023

All concomitant medications and procedures will be recorded for 21 days following each vaccination (Day 1 through Day 43); all nonstudy vaccinations and concomitant medications relevant to or for the treatment of an SAE, AESI, or MAAE will be recorded from Day 1 through Month 6 after the last study injection/EoS.

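### The alpha-controlled SCR and SRR noninferiority tests use intervals that are not adjusted for the baseline titer, which gives up a modest amount of precision

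*SAP*

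**What the plan says.** SAP 6.5 makes the seroresponse and seroconversion comparisons formal tests, gated on all six coprimaries: "The secondary endpoints on SRR and SCR will only be tested at the primary analysis at a 2-sided Type 1 error rate of 0.05". They run in a fixed sequence, influenza first: "The secondary endpoints will be tested sequentially in the following order: 1) SCR of influenza anti-HA Abs for each influenza strain". RSV-A and then RSV-B seroresponse follow, and testing stops at the first failure.

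SAP 6.4.3 sets the interval for seroconversion: "The SCR difference between the two treatment groups will be provided with 2-sided 95% CIs using the Miettinen-Nurminen's method". It sets the same method for seroresponse. The criterion there is "noninferiority of the SCR will be demonstrated if the LB of the 95% CI of the SCR difference is >-10" (percent). Protocol 9.5.1 names the same interval: "the Miettinen-Nurminen's method will be used to calculate the 95% CI for the difference in the SRR or SCR". Neither document names a covariate or stratum for these intervals, and neither plans an adjusted version as supportive.

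The coprimary models in SAP 6.4.2.1 do adjust. They use "log-transformed baseline titers as the fixed covariate, adjusted for stratified age group used for randomization".

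Baseline enters the secondary endpoints through the responder definition in SAP 3.2: "Seroconversion is defined as a postinjection titer ≥1:40 if baseline is <1:10", and otherwise as a rise of at least 4-fold. The sample exists for everyone who matters here. Appendix F states "Blood samples for humoral immunogenicity must be collected prior to administration of the study intervention on Day 1 and Day 22", and SAP 5.3 requires a baseline assessment for the PP Set.

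**The concern.** If the baseline titer predicts response, adjusting for it removes variance from the estimated difference in rates. The plan uses that information for the six GMT comparisons and leaves it out of the six responder comparisons on the same sera.

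What is at stake is power. SAP 4.3 gives power only for the GMT coprimaries, and none is stated for SCR or SRR. The four influenza tests come first and one failure ends the sequence, so lost precision there also lowers the chance of reaching the RSV tests. Trial success is not at stake, because it rests on the coprimaries alone.

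**Working it through.** **Inputs from the plan (SAP 4.3, 6.4.3):** 855 evaluable per arm, SD 1.5 of the natural-log titer, GMR 0.9, GMT margin 1.5, responder margin -10 points, two-sided 0.05.

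**Assumed, because the documents are silent:** baseline log SD 1.0 to 1.5, baseline/post correlation 0.3 to 0.7, baseline HAI GMT 10 to 40, mean rise 4-fold, 2-fold HAI dilutions, values below 1:10 set to 5.

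**1. The plan's own figure.** SE = 1.5 × √(2/855) = 0.0725. Distance to the margin = ln 1.5 + ln 0.9 = 0.300. Power = Φ(0.300/0.0725 - 1.96) = 98.5%. Six independent endpoints give 0.985^6 = 91.3%. Both stated figures reproduce.

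**2. Unadjusted responder interval.** At a 50% rate, SE = 100 × √(2 × 0.25/855) = 2.418 points, so the half-width is 1.96 × 2.418 = 4.74 points. The Miettinen-Nurminen interval computed directly also gives 4.74.

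**3. What GMR 0.9 means for the rate.** With baseline and post SD both 1.5 and correlation 0.5, the SD of the log ratio is √(1.5² + 1.5² - 2 × 0.5 × 1.5 × 1.5) = 1.5. Near a 50% rate the difference is about (ln 0.9/1.5) × 0.399 = -2.8 points.

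**4. When baseline helps.** The adjusted width is about √(1 - R²) times the unadjusted width, where R² is the share of response variance explained by baseline. For a pure 4-fold rise, R² depends on the slope of log post on log baseline, which is correlation × (post SD/baseline SD). At slope 1 baseline carries no information. For example, 0.7 × 1.5/1.0 = 1.05 gives almost no gain.

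**5. The actual SCR rule reduces the gain.** Below 1:10 the requirement is a fixed titer of 1:40. With such baselines set to 5, that is an 8-fold rise. The participants who would otherwise respond most easily face a stiffer hurdle, so response is no longer monotone in baseline. Ratio of adjusted to unadjusted width:

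| Setting | Width ratio |
|---|---|
| Pure 4-fold ratio; SD 1.5, correlation 0.5 | 0.917 |
| Actual rule, linear log baseline; same SD and correlation; baseline GMT 10, 20, 40 | 0.999, 0.988, 0.963 |
| Actual rule, linear log baseline; full assumed range | 0.92 to 1.00 |
| Actual rule, plus an indicator for baseline <1:10; full assumed range | 0.92 to 0.995 |

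A simulation of 1,500 trials (SD 1.5, correlation 0.5, 5-fold rise, true difference about -4 points) agrees. Mean width fell from 9.33 to 8.98 points (ratio 0.96), power rose from 68.4% to 71.1%, and coverage was 94.9% unadjusted and 95.4% adjusted. If correlation is allowed to fall to zero, the modelled influenza ratio reaches 0.85. I treat that as outside the working range.

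**6. Per-test power at -2.8 points and a 50% rate.** Power = Φ((10 - 2.8)/(2.418 × ratio) - 1.96).

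| Width ratio | Power |
|---|---|
| 1.00 | 0.846 |
| 0.99 | 0.853 |
| 0.96 | 0.873 |
| 0.95 | 0.880 |
| 0.92 (edge of range) | 0.899 |

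With no true difference, unadjusted power is already 98.5%.

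**The case against.** The strongest reply is that this is a preference about efficiency and not a defect. Miettinen-Nurminen is prespecified, reads the same in both documents and holds its coverage. Baseline is not ignored, since it sets each participant's threshold. The coprimaries that decide success already adjust for it. All of that stands, and it limits the point to a modest recommendation.

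A reader might go further and infer a larger gain in two ways.

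- **An 8% gain as the central case, with power 0.85 to 0.90.** This follows only if the endpoint is treated as a pure 4-fold ratio. SAP 3.2 has the separate rule for baselines below 1:10. With that rule and a linear baseline term, the same SD and correlation give 0% to 4%.
- **A large rise in the chance of passing all six tests.** Multiplying per-test powers gives 0.846^6 = 0.37 unadjusted and 0.88^6 = 0.46 at 5% narrowing. That is an upper illustration. It assumes independence, although the tests share participants and sera. It also puts every endpoint at GMR 0.9 and a 50% rate, and does not condition on the coprimaries having passed. As an example of the effect of correlation, per-test powers of 0.853 and 0.899 give 0.385 and 0.528 if independent, but 0.58 and 0.68 at a common correlation of 0.5. I place no weight on a joint figure.

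The RSV part is also weaker. SAP 6.1 defines Arm 2's RSV baseline as the Day 22 sample, taken after randomization and after Fluzone HD plus placebo. The usual robustness argument for adjustment needs a pre-randomization covariate. The influenza baseline is the Day 1 sample in both arms and meets that condition.

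**Conclusion.** The point holds as a modest, avoidable loss of efficiency, and it is clearest for the four influenza SCR tests. Under the actual SCR definition and the assumed ranges above, the adjusted interval is about 0% to 8% narrower, typically 1% to 5%. Near GMR 0.9 and a 50% rate, typical narrowing moves per-test power from about 0.85 to between 0.85 and 0.88. It would matter mainly if true differences lie around -3 to -5 points, and hardly at all if there is no true difference.

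The documents do not support a reading that these tests are biased, under-cover or put trial success at risk. The size of the gain cannot be settled from them, because they give no expected SCR, baseline SD or baseline/post correlation. I give no figure for RSV, since no case with Arm 2's Day 22 baseline was modelled.

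**What to change.** In SAP 6.4.3, for the four influenza SCR tests, keep the risk difference, the -10% margin, the test order and alpha, and use one of these:

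- **Standardization** from a logistic model with treatment, log baseline HAI titer, an indicator for baseline <1:10 and randomized age group, with a robust (influence-function) 95% CI. The indicator is needed because of the two-part definition.
- **Stratified Miettinen-Nurminen** by prespecified baseline HAI category, for example <1:10, 1:10 to <1:40, and ≥1:40.

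Report the unadjusted Miettinen-Nurminen interval as supportive.

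For RSV SRR, the same method may be used with the coprimary models' baseline, provided the SAP states that Arm 2's value is post-randomization. Alternatively, use the Day 1 sample in both arms, if it is assayed for RSV.

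For influenza the cost is SAP wording, matching text in protocol 9.5.1 and a short program, with no new data. Protocol Section 9 calls for an amendment when methods for secondary hypotheses change before unblinding, so this must be done before then. The downside is a less familiar interval.

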6.4.4. Analysis of Exploratory Immunogenicity Endpoints

The exploratory immunogenicity endpoints include the following:

- GMC and GMFR of postinjection/baseline concentration of RSV bAbs
- Proportions of participants with ≥2-fold and ≥4-fold increases in RSV bAb concentration postinjection

The following analyses may be performed:

- GMC and GMFR of RSV bAbs will be summarized descriptively in the same way as specified in Section 6.4.2.1 and Section 6.4.3.
- Proportions of participants with ≥2-fold and ≥4-fold increases in RSV bAb concentration will be summarized descriptively in the same way as specified in Section 6.4.3.

Similar definition and analysis as SRR of RSV nAbs may also be applied on SRR of RSV bAbs.

6.4.5. Subgroup Analysis

All the above specified immunogenicity analyses may be performed by the following subgroup as applicable:

- Age group (65 to <75 years, \ge 75 years)
- Sex (Male, Female)
- Race (White, Black, Asian, Other [including American Indian or Alaska Native, Native Hawaiian or other Pacific Islander and other races])
- Ethnicity (Hispanic or Latino, Not Hispanic or Latino)

All the above specified immunogenicity analyses may be performed for additional subgroups of selected baseline characteristics. If the number of participants in certain subgroups are too small, it may be combined with the other subgroups for the subgroup analyses.

6.5. Multiplicity Adjustment

A sequential/hierarchical testing procedure will be used to control the overall Type 1 error rate at 0.05 (2-sided) over the primary endpoints, and secondary endpoints.

The coprimary endpoints will be tested at the planned primary analysis at a 2-sided Type 1 error rate of 0.05. The success criteria of all 6 coprimary endpoints need to be met in order to declare the study a success to achieve noninferiority of coadministration.

The secondary endpoints on SRR and SCR will only be tested at the primary analysis at a 2-sided Type 1 error rate of 0.05 when all coprimary endpoints have achieved statistical significance. The secondary endpoints will be tested sequentially in the following order: 1) SCR of influenza anti-HA Abs for each influenza strain, 2) SRR of RSV-A nAbs and 3) SRR of RSV-B nAbs.

No further testing will be performed once the sequence/hierarch breaks, that is, further testing stops as soon as an endpoint in the sequence fails to meet success criterion of noninferiority. Analyses of remaining other secondary immune endpoints are not controlled for multiplicity.

6.6. Planned Analyses

The following analyses will be conducted on cleaned data:

1. The primary analysis of safety and immunogenicity data will be performed after all participants have completed Day 43 visit. All data relevant to the primary study analysis through the Day 43 Visit will be cleaned and locked for the primary analysis (i.e., data that are as clean as possible) and a report may be generated. The primary analysis will be performed by a separate team of unblinded programmers and statisticians.

2. The final analysis of all endpoints will be performed after all participants have completed Day 202/EoS. Results of this analysis will be presented in a final CSR.

7. Changes from Planned Analyses in Protocol

The following changes from planned analyses in the study protocol are included in this document:

• Appendix G Estimands and Estimand Specification: Estimands language has been added for primary immune endpoint and primary safety endpoint.

8. References

U.S. Department of Health and Human Services, Food and Drug Administration, Center for Biologics Evaluation and Research. Guidance for industry: Toxicity grading scale for healthy adult and adolescent volunteers enrolled in preventive vaccine clinical trials. September 2007[cited 2022 Jan 11]. Available from: https://www.fda.gov/media/73679/download.

9. List of Appendices

